### **9.2 SETTING**

#### **9.2.1 Definitions**

Study Period: the period of time that includes the exclusion criteria assessment period, baseline, cohort entry date, and follow-up period for the study population. This period is the same for all patients.

The study period will be from 1 January 2008 to 31 March 2018, encompassing date of the earliest data availability to the date of the latest data availability.

Patient Selection Period: the period of time for which patients are eligible to enter the cohort. The earliest date of the patient selection period is 17 November 2015, corresponding to 180-days after US approval date of Stiolto Respimat.

Cohort Entry Date: Date of entry to the initial cohort of Stiolto or Anoro users.

[figure not shown]
Baseline Period: the 180-day period that ends 1 day prior to the cohort entry date used to assess covariate information. The baseline period will vary between patients depending on these dates. The earliest start of the baseline period would be 21 May 2015, the date of Stiolto approval (i.e. 180 days before November 17, 2015).

Follow-Up Period: the period of time between 1 day after the cohort entry date to the earliest occurrence of the outcome (discontinuation of refills), or any censoring criteria (365 days, death, disenrollment, or end of data). Addition of another treatment in addition to index treatment will not count as discontinuation.

For entry into the study population, patients will be required to have 180 days of continuous enrolment with both medical and pharmacy coverage. Data during the baseline period will be used to confirm study eligibility and classification of incident COPD. The follow-up period will be used for capturing first and second maintenance therapies. This is illustrated in **Figure 1**.

Figure 1

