### Matched Cohort

A matched propensity score analysis will be used to assess comparative persistence between the two exposure comparison groups. Logistic regression will be used to calculate the propensity to initiate Olodaterol/Tiotropium Bromide versus Umeclidinium/Vilanterol given all covariates (except components of the Charlson Comorbidity index) listed in [section 9.3.3](#), according to the following model:

$$\text{Logit}(\text{Treatment} | X_1, X_2, \dots, X_n) = \beta_0 + \beta_1 * X_1 + \beta_2 * X_2 + \dots + \beta_n * X_n$$

Any covariates which are collinear with each other will be dropped from the analysis (if it causes failure of model to converge). The propensity score will then be used to identify up to 2 initiators of Umeclidinium/Vilanterol for each initiator of Olodaterol/Tiotropium Bromide with the same propensity score ( $\pm$  a caliper of 5%) as the corresponding initiator of Olodaterol/Tiotropium Bromide (Austin 2011).

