#### **9.3.3 Covariates**

Covariates will be identified based on data recorded within 180 days prior to or on the index date (date of dispensing/initiation of the exposure), unless otherwise specified. If multiple measurements are made in the baseline period, then the most recent measurement will be used.

Covariates will be used to predict propensity scores in later analyses. Absolute and relative frequencies of each covariate will also be reported in Table Shells 1 and 2 (see [Annex 5](#)). Detailed descriptions of the listed covariates can be found in [Annex 3](#) and [4](#).

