**Comorbidities/Symptoms**

- History of All-Cause Hospitalization
- History of Emergency Department Visit
- History of Hospitalization due to Respiratory Condition
- Acute Myocardial Infarction
- Angina Pectoris
- Peripheral Vascular Disease
- Heart Failure
- Hypertension
- Upper Respiratory Infection
- Lower Respiratory Infection
- Cardiac Arrhythmias
- Cerebrovascular Disease
- All Cancers (except nonmelanoma skin cancer)
- Allergic Rhinitis
- Chronic Sinusitis
- Bronchiectasis
- Pneumonia
- Chronic Bronchitis
- Exertional Breathlessness
- Anxiety
- Dementia
- Depression
- Osteoporosis
- Charlson Deyo Comorbidity Index
- Acute Liver Injury or Failure
- Chronic Kidney Disease (without ESRD)
- End Stage Renal Disease
- Rheumatic Disease
- Peptic Ulcer Disease
- Gastroesophageal Reflux Disease
- Type 1 Diabetes Mellitus
- Type 2 Diabetes Mellitus
- HIV/AIDS
- Hemiplegia or Paraplegia

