Peptic Ulcer Disease	
1 Inpatient or 2 Outpatient (30 – 365 days apart)
 
Diagnosis Code (Any Position), ICD-9 is any of: { “531”, “531.0”, “531.00”, “531.01”, “531.1”, “531.10”, “531.11”, “531.2”, “531.20”, “531.21”, “531.3”, “531.30”, “531.31”, “531.4”, “531.40”, “531.41”, “531.5”, “531.50”, “531.51”, “531.6”, “531.60”, “531.61”, “531.7”, “531.70”, “531.71”, “531.9”, “531.90”, “531.91”, “532”, “532.0”, “532.00”, “532.01”, “532.1”, “532.10”, “532.11”, “532.2”, “532.20”, “532.21”, “532.3”, “532.30”, “532.31”, “532.4”, “532.40”, “532.41”, “532.5”, “532.50”, “532.51”, “532.6”, “532.60”, “532.61”, “532.7”, “532.70”, “532.71”, “532.9”, “532.90”, “532.91”, “533”, “533.0”, “533.00”, “533.01”, “533.1”, “533.10”, “533.11”, “533.2”, “533.20”, “533.21”, “533.3”, “533.30”, “533.31”, “533.4”, “533.40”, “533.41”, “533.5”, “533.50”, “533.51”, “533.6”, “533.60”, “533.61”, “533.7”, “533.70”, “533.71”, “533.9”, “533.90”, “533.91”, “534”, “534.0”, “534.00”, “534.01”, “534.1”, “534.10”, “534.11”, “534.2”, “534.20”, “534.21”, “534.3”, “534.30”, “534.31”, “534.4”, “534.40”, “534.41”, “534.5”, “534.50”, “534.51”, “534.6”, “534.60”, “534.61”, “534.7”, “534.70”, “534.71”, “534.9”, “534.90”, “534.91” }
 
Diagnosis Code (Any Position), ICD-10 is any of: { “K25.0”, “K25.1”, “K25.2”, “K25.3”, “K25.4”, “K25.5”, “K25.6”, “K25.7”, “K25.9”, “K26.0”, “K26.1”, “K26.2”, “K26.3”, “K26.4”, “K26.5”, “K26.6”, “K26.7”, “K26.9”, “K27.0”, “K27.1”, “K27.2”, “K27.3”, “K27.4”, “K27.5”, “K27.6”, “K27.7”, “K27.9”, “K28.0”, “K28.1”, “K28.2”, “K28.3”, “K28.4”, “K28.5”, “K28.6”, “K28.7”, “K28.9” }

Gastroesophageal Reflux Disease	
Any of the following criteria:
 
≥2 medical claims with a primary or secondary ICD-9-CM code for reflux esophagitis (530.11), esophageal reflux (530.81) or heartburn (787.1) or primary or secondary ICD-10-CM code for GERD (K21, K21.0, K21.9) or Heartburn (R12); ≥1 medical claim with a primary or secondary ICD-9-CM 530.11, 530.81 or 787.1 and either (a) ≥1 pharmacy claim for a PPI (esomeprazole, lansoprazole, omeprazole, pantoprazole, rabeprazole), an H2RA (cimetidine, famotidine, nizatidine, or ranitidine) or “other” GERD agent (bethanechol, metoclopramide, sucralfate) or (b) ≥1 medical claim with a primary or secondary ICD-9-CM code for esophageal stricture (530.3) Barrett’s esophagus (530.85), esophageal ulcer (530.2x) or esophagitis (530.1x).

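### The GERD definition in Annex 4 accepts ICD-10 codes only in its two-claim criterion, so one ICD-10 GERD claim plus a supporting drug fill or complication claim does not count

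*Combined protocol and SAP*

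**What the plan says.** Annex 4 gives two criteria for GERD, and meeting either is enough.

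- **Criterion 1** needs at least two medical claims. It accepts ICD-9 530.11, 530.81 or 787.1, or a "primary or secondary ICD-10-CM code for GERD (K21, K21.0, K21.9) or Heartburn (R12").
- **Criterion 2** needs at least one "medical claim with a primary or secondary ICD-9-CM 530.11, 530.81 or 787.1 and either" (a) or (b). Part (a) is a drug fill: a "pharmacy claim for a PPI (esomeprazole, lansoprazole, omeprazole, pantoprazole, rabeprazole"), an H2-receptor antagonist or another listed agent. Part (b) is a further diagnosis claim with a "primary or secondary ICD-9-CM code for esophageal stricture (530.3"), or for Barrett's oesophagus (530.85), oesophageal ulcer (530.2x) or oesophagitis (530.1x). Neither the anchor claim nor part (b) has an ICD-10 code.

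"Gastroesophageal Reflux Disease" is on the comorbidity list in section 9.3.3. The Matched Cohort text in section 9.2.2 fits the propensity score "given all covariates (except components of the Charlson Comorbidity index) listed in" that section. The Charlson-Deyo entry in Annex 4 does not count GERD as a component, so GERD stays in. The multivariable Cox and logistic models in section 9.7.1.3 follow the same rule.

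On timing, section 9.3.3 says "Covariates will be identified based on data recorded within 180 days prior to or on the index date", and the GERD entry sets no other look-back. Section 9.2.1 adds that "The earliest start of the baseline period would be 21 May 2015".

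**The concern.** The same clinical picture is classified differently according to the coding system on the claim. Criterion 1 and the other legible diagnosis definitions in Annex 4 list both systems, so this looks like an incomplete update and not a deliberate choice.

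The rest of the covariate set does not directly replace what is lost. Acid-suppressing drugs are not among the concomitant medications in section 9.3.3 or Annex 3. Peptic ulcer disease is a Charlson component, so it leaves the models as a separate term. The balance tables in Annex 5 (Tables 2 and 3) would be computed on the incompletely recorded variable, so they cannot show whether the arms are balanced on GERD under the fuller definition.

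At stake is the completeness of one covariate among many that section 9.12 puts forward as confounders. In sensitivity analysis 3 its comparability across entry dates is also affected.

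**Working it through.** **1. The two criteria side by side**

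| Baseline record | Criterion 1 | Criterion 2 | Classed as |
|---|---|---|---|
| One 530.81 claim, one PPI fill | not met | met by (a) | GERD |
| One K21 claim, one PPI fill | not met | not met | no GERD |
| Two K21 claims | met | not needed | GERD |

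The gap concerns patients with exactly one ICD-10 GERD claim in the look-back plus a supporting fill or complication claim.

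**2. Entry dates affected in the primary cohort**

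Inputs from the documents: entry from 17 November 2015 to 31 March 2018, which is 866 days, and a look-back of 180 days. As a check, 17 November 2015 minus 180 days is 21 May 2015, which agrees with section 9.2.1. Assumptions: US claims changed to ICD-10 on 1 October 2015, and entry is even over calendar days.

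The look-back lies wholly after the changeover when entry is on or after 1 October 2015 + 180 days = 29 March 2016. From then to 31 March 2018 there are 733 days, and 733/866 = 84.6%. The other 133 entry dates (133/866 = 15.4%) have some ICD-9 look-back. Counted by day, 5.7% of all look-back days precede the changeover.

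**3. Sensitivity analysis 3**

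Section 9.7.2 starts entry on 21 May 2015, which adds 180 entry dates: 866 + 180 = 1,046. All the added dates have some ICD-9 look-back: 133 + 180 = 313, and 313/1,046 = 29.9%.

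**4. Range over the assumed changeover date**

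| Assumed changeover | Primary: criterion 2 unreachable | Primary: some ICD-9 look-back | Sensitivity analysis 3: some ICD-9 look-back |
|---|---|---|---|
| 1 July 2015 | 825/866 = 95.3% | 41/866 = 4.7% | 221/1,046 = 21.1% |
| 1 October 2015 | 733/866 = 84.6% | 133/866 = 15.4% | 313/1,046 = 29.9% |
| 1 January 2016 | 641/866 = 74.0% | 225/866 = 26.0% | 405/1,046 = 38.7% |

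**5. Possible size, for illustration only**

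The documents give no GERD prevalence and no share of patients with a single claim. Assume a prevalence of 22% in one arm and 18% in the other, no false positives, and a definition that finds a fraction s of GERD patients in both arms. After exact balance on recorded GERD, the remaining difference in true GERD is

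(1 − 0.22s) × [0.22(1 − s)/(1 − 0.22s) − 0.18(1 − s)/(1 − 0.18s)].

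- s = 0.80: 0.824 × (0.0534 − 0.0421) = 0.009, or 0.9 percentage points.
- s = 0.50: 0.890 × (0.1236 − 0.0989) = 0.022, or 2.2 percentage points.

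Divided by √(0.2 × 0.8) = 0.4, these are standardized differences of about 0.02 and 0.055. For the larger one, if GERD raised the discontinuation hazard by 20% (assumed), the hazard ratio would shift by about (1 + 0.2 × 0.220)/(1 + 0.2 × 0.198) = 1.004. If it raised the hazard by 50%, the shift would be about 1.110/1.099 = 1.01.

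**The case against.** The strongest reply is that GERD remains usable. Two claims is close to the rule for most Annex 4 diagnoses (one inpatient claim, or two outpatient claims 30 to 365 days apart), and it is looser on spacing. Patients with two ICD-10 claims are still found. This stands: the loss is partial, and it is a loss only relative to the definition's own ICD-9 rule.

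A reader might infer that GERD becomes a proxy for calendar time in the primary analysis. The documents do not support that. If most primary look-backs lie wholly after the changeover, most patients are judged by the one two-claim rule, and little variation by era is left. Year of cohort entry is also in the propensity score. It is a coarse control, because the 133 mixed entry dates all fall within its first level (17 November 2015 to 30 November 2016). The argument about coding era belongs mainly to sensitivity analysis 3.

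It can also be said that review is already planned. Section 9.12 has medical reviewers check code lists before implementation, and section 9.8 allows definitions to be modified. Those provisions are where the omission could be caught, but they do not supply the missing codes.

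**Conclusion.** The inconsistency stands on the text alone and needs no outside figure: criterion 2 cannot be met by an ICD-10 anchor claim. With an assumed changeover on 1 October 2015 and even entry, that closes criterion 2 for 85% of primary entry dates (74% to 95% for changeover dates three months either side), so GERD is captured there almost only by two claims. In sensitivity analysis 3 the share of entry dates with some ICD-9 look-back is 30% against 15%, so measurement differs more by coding era there.

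A reader might infer that much of the confounding by GERD survives matching, or that the primary hazard ratio is materially biased. Neither follows. The number of patients missed cannot be computed from the documents, nothing shows that the loss differs by arm, and the illustration leaves an imbalance of about 0.9 to 2.2 percentage points on one covariate among many. The effect on the hazard ratio is expected to be very small. This is a minor correction, worth making because it is cheap.

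**What to change.** In the GERD entry of Annex 4:

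- Add K21, K21.0, K21.9 and R12 to the anchor claim of the second criterion. They are already listed in the first.
- Add the ICD-10 equivalents of 530.3, 530.85, 530.2x and 530.1x to part (b), and have them confirmed in the code-list review that section 9.12 plans.
- Record the change as a protocol amendment, as section 9.8 requires.

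The cost is the amendment and a rerun of the GERD covariate, the propensity score and matching, and the models that use it. Specificity may fall slightly, because one R12 (heartburn) claim plus an acid-suppressant fill would then qualify. The ICD-9 rule already accepts the same combination through 787.1, so the change makes the two coding systems consistent and does not introduce a new kind of case.

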Charlson-Deyo Comorbidity Index	
This measure computes a score by summing over the following components:
 
 
· If the event Acute Myocardial Infarction Occurs within 180 days, set the score to 1.0 Otherwise, set the score to 0.0
 
· If the event Heart Failure Occurs within 180 days, set the score to 1.0 Otherwise, set the score to 0.0
 
· If the event Peripheral Vascular Disease Occurs within 180 days, set the score to 1.0 Otherwise, set the score to 0.0
 
· If the event Cerebrovascular Disease Occurs within 180 days, set the score to 1.0 Otherwise, set the score to 0.0
 
· If the event Dementia Occurs within 180 days, set the score to 1.0 Otherwise, set the score to 0.0
 
· If the event Chronic Obstructive Pulmonary Disease Occurs within 180 days, set the score to 1.0 Otherwise, set the score to 0.0
 
· If the event Rheumatologic Disease Occurs within 180 days, set the score to 1.0 Otherwise, set the score to 0.0
 
· If the event Peptic Ulcer Disease Occurs within 180 days, set the score to 1.0 Otherwise, set the score to 0.0
 
· If the event Hemiplegia or Paraplegia Occurs within 180 days, set the score to 2.0 Otherwise, set the score to 0.0
 
· If the event Renal Disease Occurs within 180 days, set the score to 2.0 Otherwise, set the score to 0.0
 
· If the event HIV/AIDS Occurs within 180 days, set the score to 6.0 Otherwise, set the score to 0.0
 
· For the measure Cancer use the value of the measure as the score multiplied by weight 1.0 If the value is missing, set the score to 0.0
 
· For the measure Diabetes use the value of the measure as the score multiplied by weight 1.0 If the value is missing, set the score to 0.0
 
· For the measure Liver Disease use the value of the measure as the score multiplied by weight 1.0 If the value is missing, set the score to 0.0
 

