Type 1 Diabetes Mellitus	
1 Inpatient or 2 Outpatient (30 – 365 days apart)
 
Diagnosis Code (Any Position), ICD-9 is any of: { “250.11”, “250.13”, “250.21”, “250.23”, “250.31”, “250.33”, “250.41”, “250.43”, “250.51”, “250.53”, “250.61”, “250.63”, “250.71”, “250.73”, “250.81”, “250.83”, “250.91”,

	
“250.93”, “250.01”, “250.03” }
 
Diagnosis Code (Any Position), ICD-10 is any of: { “E10”, “E10.1”, “E10.10”, “E10.11”, “E10.2”, “E10.21”, “E10.22”, “E10.29”, “E10.3”, “E10.31”, “E10.311”, “E10.319”, “E10.32”, “E10.321”, “E10.329”, “E10.33”, “E10.331”, “E10.339”, “E10.34”, “E10.341”, “E10.349”, “E10.35”, “E10.351”, “E10.359”, “E10.36”, “E10.39”, “E10.4”, “E10.40”, “E10.41”, “E10.42”, “E10.43”, “E10.44”, “E10.49”, “E10.5”, “E10.51”, “E10.52”, “E10.59”, “E10.6”, “E10.61”, “E10.610”, “E10.618”, “E10.62”, “E10.620”, “E10.621”, “E10.622”, “E10.628”, “E10.63”, “E10.630”, “E10.638”, “E10.64”, “E10.641”, “E10.649”, “E10.65”, “E10.69”, “E10.8”, “E10.9” }

Type 2 Diabetes Mellitus	
1 Inpatient or 2 Outpatient (30 – 365 days apart)
 
Diagnosis Code (Any Position), ICD-9 is any of: { “250.00”, “250.02”, “250.10”, “250.12”, “250.20”, “250.22”, “250.30”, “250.32”, “250.40”, “250.42”, “250.50”, “250.52”, “250.60”, “250.62”, “250.70”, “250.72”, “250.80”, “250.82”, “250.90”, “250.92” }
 
Diagnosis Code (Any Position), ICD-10 is any of: { “E11.00”, “E11.01”, “E11.21”, “E11.29”, “E11.311”, “E11.319”, “E11.36”, “E11.39”, “E11.40”, “E11.51”, “E11.618”, “E11.620”, “E11.621”, “E11.622”, “E11.628”, “E11.630”, “E11.638”, “E11.641”, “E11.649”, “E11.65”, “E11.69”, “E11.8”, “E11.9”, “E13.10” }

Type 1 or Type 2 Diabetes without Complications	
1 Inpatient or 2 Outpatient (30 – 365 days apart)
 
Diagnosis Code (Any Position), ICD-9 is any of: { “250.0”, “250.00”, “250.01”, “250.02”, “250.03”, “250.1”, “250.10”, “250.11”, “250.12”, “250.13”, “250.2”, “250.20”, “250.21”, “250.22”, “250.23”, “250.3”, “250.7”, “250.70”, “250.71”, “250.72”, “250.73”, “249.0”, “249.00”, “249.01” }
 
Diagnosis Code (Any Position), ICD-10 is any of: { “E10.1”, “E10.6”, “E10.8”, “E10.9”, “E11.0”, “E11.6”, “E11.8”, “E11.9”, “E13.0”, “E13.1”, “E13.6”, “E13.8”, “E13.9” }

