Type 1 or Type 2 Diabetes with Complications	
1 Inpatient or 2 Outpatient (30 – 365 days apart)
 
Diagnosis Code (Any Position), ICD-9 is any of: { “250.4”, “250.40”, “250.41”, “250.42”, “250.43”, “250.5”, “250.50”, “250.51”, “250.52”, “250.53”, “250.6”, “250.60”, “250.61”, “250.62”, “250.63”, “250.3”, “250.30”, “250.31”, “250.32”, “250.33” }
 
Diagnosis Code (Any Position), ICD-10 is any of: { “E10.2”, “E10.21”, “E10.22”, “E10.29”, “E10.3”, “E10.31”, “E10.311”, “E10.319”, “E10.32”, “E10.321”, “E10.329”, “E10.33”, “E10.331”, “E10.339”, “E10.34”, “E10.341”, “E10.349”, “E10.35”, “E10.351”, “E10.359”, “E10.36”, “E10.39”, “E10.4”, “E10.40”, “E10.41”, “E10.42”, “E10.43”, “E10.44”, “E10.49”, “E10.5”, “E11.2”, “E11.21”, “E11.22”, “E11.29”, “E11.3”, “E11.31”, “E11.311”, “E11.319”, “E11.32”, “E11.321”, “E11.329”, “E11.33”, “E11.331”, “E11.339”, “E11.34”, “E11.341”, “E11.349”, “E11.35”, “E11.351”, “E11.359”, “E11.36”, “E11.39”, “E11.4”, “E11.40”, “E11.41”, “E11.42”, “E11.43”, “E11.44”, “E11.49”, “E11.5”, “E13.4”, “E13.40”, “E13.41”, “E13.42”, “E13.43”, “E13.44”, “E13.49”, “E13.5” }

Mild Liver Disease	
1 Inpatient or 2 Outpatient (30 – 365 days apart)
 
Diagnosis Code (Any Position), ICD-9 is any of: { “571.2”, “571.4”, “571.40”, “571.41”, “571.42”, “571.49”, “571.5”, “571.6” }
 
Diagnosis Code (Any Position), ICD-10 is any of: { “B18.0”, “B18.1”, “B18.2”, “B18.8”, “B18.9”, “K70.0”, “K70.1”, “K70.10”, “K70.11”, “K70.2”, “K70.3”, “K70.9”, “K71.3”, “K71.4”, “K71.5”, “K71.7”, “K73.0”, “K73.1”, “K73.2”, “K73.8”, “K73.9”, “K74.0”, “K74.1”, “K74.2”, “K74.3”, “K74.4”, “K74.5”, “K74.6”, “K74.60”, “K74.69”, “K76.0”, “K76.2”, “K76.3”, “K76.4”, “K76.8”, “K76.9”, “Z94.4” }

Moderate/Severe Liver Disease	
1 Inpatient or 2 Outpatient (30 – 365 days apart)
 
Diagnosis Code (Any Position), ICD-9 is any of: { “456.0”, “456.1”, “456.2”, “456.20”, “456.21”, “572.2”, “572.3”, “572.4”, “572.8” }
 
Diagnosis Code (Any Position), ICD-10 is any of: { “I85.0”, “I86.4”, “K70.4”, “K71.1”, “K72.1”, “K72.9”, “K76.5”, “K76.6”, “K76.7” }

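### Annex 4's Type 2 diabetes list omits 14 full E11 codes that its with-complications row counts, and the four diabetes rows do not fit together

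*Combined protocol and SAP*

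**What the plan says.** Annex 4 has four diabetes rows. Each requires 1 inpatient claim, or 2 outpatient claims 30 to 365 days apart.

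- **Type 2 Diabetes Mellitus.** The 24 ICD-10 codes begin "E11.00”, “E11.01”, “E11.21”, “E11.29”, “E11.311”, “E11.319”, “E11.36”, “E11.39”, “E11.40”, “E11.51”, “E11.618". The 20 ICD-9 codes end "250.70”, “250.72”, “250.80”, “250.82”, “250.90”, “250.92".
- **Type 1 Diabetes Mellitus.** A long E10 list with headings and children, and the ICD-9 250.x1/250.x3 codes.
- **Type 1 or Type 2, with complications.** 68 ICD-10 entries, 30 of them E11, including "E11.40”, “E11.41”, “E11.42”, “E11.43”, “E11.44”, “E11.49”, “E11.5". The ICD-9 part includes 250.3 and 250.30-250.33.
- **Type 1 or Type 2, without complications.** 13 four-character ICD-10 codes, among them "E11.0”, “E11.6”, “E11.8”, “E11.9”, “E13.0”, “E13.1”, “E13.6”, “E13.8”, “E13.9". The ICD-9 part ends "250.3”, “250.7”, “250.70”, “250.71”, “250.72”, “250.73”, “249.0”, “249.00”, “249.01".

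Type 1, Type 2 and the Charlson-Deyo index are covariates in section 9.3.3; the two complication rows are not. Section 9.2.2 (Matched Cohort) fits the propensity model "given all covariates (except components of the Charlson Comorbidity index) listed in" that section. The diabetes term of the Charlson entry in Annex 4 reads: "For the measure Diabetes use the value of the measure as the score multiplied by weight 1.0". Tables 2 and 3 report all four diabetes rows.

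**The concern.** A claim that counts as complicated Type 1 or Type 2 diabetes should also count as Type 1 or Type 2 diabetes, and the printed lists do not ensure this. The Type 2 row includes E11.40 but not E11.41 to E11.44 or E11.49, and E11.21 and E11.29 but not E11.22. The Type 1 row prints the E10 counterpart of every one of these.

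Two things are at stake. First, the Type 2 flag is a named covariate and, unless dropped as a Charlson component, enters the propensity model and the multivariable models. Second, the secondary objective of characterising new users would show diabetes rows that contradict each other.

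**Working it through.** **1. With-complications row against Type 2 row.** Both ICD-10 lists come from Annex 4.

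- E11 entries in the with-complications row: 30.
- Also in the Type 2 row: 7 (E11.21, .29, .311, .319, .36, .39, .40).
- Not in the Type 2 row: 30 − 7 = 23.
- Of these, 9 are headings (E11.2, .3, .31, .32, .33, .34, .35, .4, .5) and 14 are full codes: E11.22, .321, .329, .331, .339, .341, .349, .351, .359, .41, .42, .43, .44, .49.

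Prefix matching recovers none of the 14, because the Type 2 row prints no E11, E11.2, E11.3 or E11.4 parent and no wildcard. All 30 E10 entries of the with-complications row are in the Type 1 row.

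**2. Type 1 and Type 2 rows against the two complication rows.**

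- ICD-9, either matching rule: 250.80, .82, .90, .92 (Type 2) and 250.81, .83, .91, .93 (Type 1) are in neither complication row.
- ICD-10, exact matching only: 15 of the 24 Type 2 codes are in neither row (E11.00, .01, .51, .618, .620, .621, .622, .628, .630, .638, .641, .649, .65, .69 and E13.10), as are 22 Type 1 entries. Under prefix matching no Type 2 code is left out, and only the bare heading E10 for Type 1.
- Overlap: 250.3 is printed in both complication rows. Under prefix matching this puts 250.30-250.33 in both; under exact matching only the literal heading is shared.

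Exact matching is the plainer reading, because Annex 4 writes an asterisk where it wants a wildcard (R06.0*, O98.7*) and the with-complications row lists parents and children separately. The rule itself is not stated.

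**3. What this does to patients.** Take outpatient claims 30 to 365 days apart, with no inpatient claim:

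| Claims | Type 1 | Type 2 | Without | With |
|---|---|---|---|---|
| E11.42 twice | no | no | no | yes |
| E11.9 once, E11.42 once | no | no | no | no |
| E11.65 twice | no | yes | exact no, prefix yes | no |
| 250.80 twice | no | yes | no | no |

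The second line shows that the loss is not confined to patients coded solely with omitted codes: the two-claim rule also drops patients whose claims are split between listed and omitted codes.

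**4. Route to the propensity model.** The plan does not say whether Type 2 is dropped as a Charlson component, nor which rows build the Charlson diabetes measure.

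- If the complication rows feed it, an E11.42-only patient still scores for diabetes, while a 250.80-only patient does not.
- If the Type 1 and Type 2 rows feed it, an E11.42-only patient does not score.
- In every case insulin and antidiabetic agents are separate covariates (section 9.3.3).

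**5. Illustrative size.** The documents give no frequencies, so these inputs are assumptions: type 2 prevalence 25-30%, and 10-25% of those patients missed by the Type 2 row (sensitivity s = 0.90 to 0.75). The true missed share could be nearer zero.

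- Olodaterol/tiotropium initiators (3,889, section 9.5) flagged no in error: 3,889 × 0.25 × 0.10 = 97, to 3,889 × 0.30 × 0.25 = 292.
- Suppose the arms truly differ by 3 points (p1 = 0.25 or 0.30; p0 = 0.22 or 0.27), specificity is 1 and the recorded flag is exactly balanced. The fraction of the difference left is (1 − s)/(1 − s·p0). For s = 0.90 it is 0.10/0.802 = 12% and 0.10/0.757 = 13%. For s = 0.75 it is 0.25/0.835 = 30% and 0.25/0.7975 = 31%.
- In points: 0.125 × 3 = 0.4 to 0.313 × 3 = 0.9. Dividing by √(0.25 × 0.75) = 0.43 and √(0.30 × 0.70) = 0.46 gives standardised differences of about 0.01 to 0.02, before any credit to the other covariates.

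**The case against.** The strongest reply is that the lists differ as described but little follows from it. The protocol nowhere says that the rows must nest; the complication rows include E13 and ICD-9 249.0x codes, so they are broader than Type 1 plus Type 2. The Charlson index stays in the propensity model whatever happens to its components. The ICD-10 reverse gap needs exact matching, whereas the 250.3 overlap does harm mainly under prefix matching, so the two cannot be added together. Primary-analysis baselines start no earlier than 21 May 2015, and nothing shows that ICD-9 claims are common in them. Section 9.12 already promises review of code lists by qualified medical reviewers, and section 9.8 allows definitions to be modified.

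Much of this stands, and it limits the consequences. It rules out two readings that a reader might infer. One is that patients with complicated type 2 diabetes are matched as non-diabetic: that does not follow, since they may score through the Charlson index and may be captured by the medication covariates. The other is that the Charlson score is itself shown to be wrong: the documents never say which rows feed it, and taking the complication rows as the source is only an inference.

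The reply does not remove the 14-code gap. That gap holds under either matching rule, whatever was intended, and it makes a row titled Type 1 or Type 2 diabetes count patients who have neither by the plan's own definitions. A promise of review does not correct the list that the protocol prints.

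**Conclusion.** The point holds as an internal inconsistency in the code lists. The Type 2 covariate, and the diabetes rows of Tables 2 and 3, misclassify identifiable patients through 14 omitted full codes. The ICD-9 250.8x/250.9x gap in the complication rows is also independent of the matching rule. The further ICD-10 gap in those rows depends on exact matching, and any effect on the Charlson score depends on an unstated source.

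The effect on the primary hazard ratio is probably small. Under the assumed frequencies and an assumed 3-point difference between arms, the leftover imbalance is under one percentage point. No such difference is shown, so a claim that the primary comparison is biased in a particular direction would go beyond the documents. The change is worth making because the error is plain and the correction cheap.

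**What to change.** In Annex 4:

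1. Define Type 2 diabetes as E11.* plus the existing E13.10 and ICD-9 250.x0/250.x2 codes. If explicit listing is preferred, adding the 14 full codes takes the ICD-10 list from 24 to 38.
2. State whether matching is exact or by prefix.
3. State which rows feed the Charlson diabetes measure, and whether the Type 1 and Type 2 flags count as Charlson components for sections 9.2.2 and 9.7.1.3.
4. Place every Type 1 and Type 2 code in exactly one complication row, including 250.8x, 250.9x, E13.10 and the children of E10/E11 .0, .1, .5 and .6. The medical code reviewers named in section 9.12 should decide which row.
5. Print 250.3 in one complication row only.

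No new data are needed. Section 9.8 requires the change to be documented in an amendment. The milestones in section 6 put the final tables at 26 April 2019, before this version's date of 22 November 2019. If the analysis has already been run, the cost is rebuilding the flags, refitting the propensity model, rematching and rerunning the tables.
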